5.7.2 Handling of Participant Withdrawals or Termination

As a pragmatic trial, it is accepted that enrolled children – who are students at participating schools – may be lost to follow-up (e.g., moved away, enrolled in another school, or other reason). As a result, no attempts will be made to follow-up with withdrawn or terminated participants.

5.8 Premature Termination or Suspension of Study

This study may be temporarily suspended or prematurely terminated if there is sufficient reasonable cause. Written notification, documenting the reason for study suspension or termination, will be provided by the suspending or terminating party to Principal Investigator [name] and the National Institutes of Minority Health and Health Disparities (funder). If the study is prematurely terminated or suspended, the PI will promptly inform the IRB and will provide the reason(s) for the termination or suspension.

Circumstances that may warrant termination or suspension include, but are not limited to:

- Determination of unexpected, significant, or unacceptable risk to participants
- Demonstration of efficacy that would warrant stopping
- Insufficient compliance to protocol requirements
- Data that are not sufficiently complete and/or evaluable
- Determination of futility

Study may resume once concerns about safety, protocol compliance, data quality are addressed and satisfy the sponsor, IRB and/or FDA.

6 Study Agent and/or Procedural Intervention

6.1.1 Acquisition

All study agents will be purchased directly from their respective manufacturers or approved dental suppliers:

1. Advantage Arrest is manufactured and distributed by Elevate Oral Care.
2. Fluoride Varnish is acquired from standard dental supply vendors.
3. GC Fuji IX is produced by GC America and is purchased through commercial dental distributors.

Study products will be stored and handled by the principal investigator and study staff at the clinical site.

6.1.2 Formulation, Appearance, Packaging, and Labeling

All products are commercially marketed and labeled appropriately for human dental use. No relabeling or repackaging will be conducted.

1. Advantage Arrest™: 38% Silver Diamine Fluoride. Dark blue liquid in 8 mL dropper bottles. Supplied in labeled, sealed containers from Elevate Oral Care.
2. Fluoride Varnish: 5% Sodium Fluoride. Dispensed in single-use packets or “lollipacks.” Viscous pale yellow gel.
3. GC Fuji IX: pre-capsulated glass ionomer restorative material. Self-curing. Provided in labeled blister packaging.

6.1.3 Product Storage and Stability

All agents will be stored according to manufacturer recommendations:

1. Advantage Arrest: Store at room temperature, protected from light. Stable until expiration if unopened. Shelf life ~2 years. Stored in a combination-locked mobile chest.
2. Fluoride Varnish: Store at room temperature. Single-use packets or “lollipacks” are stable until expiration. Stored in a combination-locked mobile chest.
3. GC Fuji IX: Store in a cool, dry area. Once a capsule is activated, it must be used immediately.

All opened multi-dose products (if applicable) will be discarded per manufacturer's guidelines and local infection control policy.

6.1.4 Preparation

All preparation will be done by licensed dental professionals or trained study staff under clinical supervision.

1. Advantage Arrest: No reconstitution. Applied directly using microbrush applicators.
2. Fluoride Varnish: Dispensed from single-use packets or “lollipacks”. No preparation needed.
3. GC Fuji IX: Mixed using an amalgamator per manufacturer's instructions.

6.1.5 Dosing and Administration

Doses are not weight-based. All products are administered by licensed dental professionals or trained study staff under clinical supervision during the clinical visit which takes place during traditional school hours. There are no self-administered components.

1. Advantage Arrest: 1-2 drops are dispensed to a dappen dish or mixing well and applied per site with a microbrush, once per lesion or sound tooth. Application time: ~30 seconds scrubbing with a minimum 1-minute drying time.
2. Fluoride Varnish: Applied to all tooth surfaces post-cleaning. 0.3-.4mL per child. Applied with brush, allowed to set with saliva.
3. GC Fuji IX: Mixed and placed into cavities using appropriate applicators and finger-sweep technique. Sets chemically in under 6 minutes.

6.1.6 Route of Administration

All products are administered **topically to teeth** in the oral cavity.

6.1.7 Starting Dose and Dose Escalation Schedule

All products will be used at standard clinical dosages as indicated for routine application. No dose escalation will occur.

6.1.8 Dose Adjustments/Modifications/Delays

Dose modifications are not anticipated. If a participant develops hypersensitivity, ulceration, or other adverse effects, the product will be discontinued. Adverse reactions are expected to be rare but will be monitored.

6.1.9 Duration of Therapy

Participants will be followed for up to five visits post-treatment for outcome evaluation and re-/treatment.

1. Advantage Arrest: Single-visit placement or bi-annual application in line with protocol
2. Fluoride Varnish: Bi-annual application
3. GC Fuji IX: Single-visit placement or bi-annual evaluation for retention and replacement as needed, in line with protocol.

6.1.10 Tracking of Dose

Applications will be documented in a secure (NESS) dental chart. Each agent's use per visit will be recorded with tooth number, location of lesion (as applicable), and operator name and signature. Regular reconciliation will confirm accuracy.

6.1.11 Device Specific Considerations

Not applicable – No devices are being tested in this study.

6.2 Study Agent Accountability Procedures

All study products will be tracked using a supply inventory tracker maintained by study staff. This log will include:

1. Expiration date
2. Quantity received
3. Remaining inventory

Unused or expired product will be discarded per manufacturer and site policy. No products will be returned to the manufacturer. Reconciliation will be conducted monthly and at study closeout.

6.3 Study Procedural Intervention(s) Description

The procedural interventions in this study include non-invasive caries arrest and restoration treatments:

1. Topical application of silver diamine fluoride
2. Application of fluoride varnish
3. Placement of atraumatic restorations (ART) using GC Fuji IX

Each is delivered during routine clinical visits by licensed dental providers in accordance with the manufacturer's instructions.

6.3.1 Administration of Procedural Intervention

All interventions will be administered by licensed dentists or dental hygienists. Any individuals administering the intervention (those individuals providing care as part of the SCHOOL-BASED DENTAL PROGRAM) will be first added to the study and approved as investigators prior to their involvement.

Each visit will last approximately 7-12 minutes, on average. Fluoride varnish may be reapplied at 6-month intervals. Silver diamine fluoride and sealants or ART with Fuji IX will be placed during the initial and subsequent 6-month intervals, with bi-annual evaluation for retention and replacement as needed, in line with protocol. At least 5 visits are proposed for participants in this study.

6.3.2 Procedures for Training of Clinicians on Procedural Intervention

All participating clinicians will be trained and standardized before enrolling participants. A standard operating procedure (SOP) will be developed and distributed. Periodic training and standardization sessions will occur every 12 months to ensure procedural consistency. Training and standardization exercises will involve the use of case reports and relevant intraoral images, typodonts, and live patients not included in the study.

6.3.3 Assessment of Clinician and/or Participant Compliance with Study Procedural Intervention

There is no assessment of participant compliance, as all treatments are provided by the school-based caries prevention program. Clinician compliance will be assessed by comparing the de-identified electronic health record data with the corresponding pathway from the research design. Any evidence of mis-match between what patients should have received and actually received will be recorded, noted in study notebooks, and communicated to the school-based caries prevention program.

7 Study Procedures and Schedule

7.1 Study Procedures/Evaluations

All treatments listed in the schematic for the BASICS experimental study are already provided by participation in the school-based caries prevention program. Thus, procedures described in section 7.1.1 are already established

in the program. In this proposed study, we will be changing the order of treatments based on the longitudinal oral health needs of participants. Thus, the research component of this study is to explore the impact of the variation in treatment scheduling and sequence on oral health.

All of the included procedures can be expected to be provided outside of the study, but the study specific procedures will modify the order of the procedures that are provided.

7.1.1

Study Specific Procedures

While the following procedure are provided as part of the operations of the SBCP, they are included as study-specific as well as these are the accepted procedures for the treatments selected for the study.

At each study visit, a clinician will perform full-mouth visual-tactile oral examinations using a disposable mirror, disposable explorer, and head lamp with participants laying in a portable dental chair. Teeth will be assessed as being present or missing intraorally. Individual tooth surfaces will be assessed as being intact/sound, sealed, restored, decayed, or arrested. Caries diagnosis will use the International Caries Detection and Assessment System (ICDAS) scoring criteria for 5 (distinct cavity with visible dentine) or 6 (extensive distinct cavity with visible dentine) [27, 28].

At the baseline observation, the enrolled population will be randomized to receive a first-stage treatment of either silver diamine fluoride (Trajectory 1) or dental sealants with atraumatic restorations, where indicated (Trajectory 2). Children in the initial SDF group will receive the treatment on sound posterior dentition and any posterior teeth with untreated decay. Children in the sealant and ART group will receive either treatment on posterior dentition based on the presence of untreated caries. In both groups, treatment will be applied in the absence of pain, abscess, or infection

Nonresponse will be determined at the second and third post-baseline observational periods by the diagnosis of any dental caries on posterior dentition, including any new caries on previously sound dentition (primary prevention failure) or any teeth diagnosed at baseline with caries that failed to demonstrate arrest (secondary prevention failure). The total number of caries will also be recorded. Responders to either first stage treatment will continue to receive biannual screenings for retention and responsiveness. Non-responders will subsequently proceed to second-stage randomization.

Nonresponders in Trajectory 1 will receive a second-stage randomization to either SDF reapplication plus fluoride varnish receipt of an electronic toothbrush, or an SDF reapplication plus dental sealants. As nonresponse is determined by the diagnosis of new caries, this latter pathway will take the form of delayed silver-modified atraumatic restorative treatment (delayed SMART) [22, 23] on any affected teeth and application of sealants to any remaining sound dentition. Similarly, nonresponders in Trajectory 2 will be randomized to either an augmented treatment of sealant reapplication (including atraumatic restorations) plus fluoride varnish and receipt of an electronic toothbrush or an intensified protocol of SMART on affected dentition. Caries incidence will continue to be evaluated at each remaining planned observation.

Additional design procedures include (1) any patients with sealants that are not retained but no decay is indicated will be considered responsive and the sealant will be reapplied; (2) any patients with atraumatic restorations that are not retained will be considered non-responsive, as it cannot be robustly determined if there is no new decay; (3) any responding participant who transitions to nonresponse after the predetermined nonresponse periods will continue to receive their original first-stage intervention and the total days that elapsed before nonresponse was observed will be recorded; (4) any nonresponding patient who continues to fail to respond will receive reapplication/reinforcement of their second-stage intervention; (5) any new dentition that erupts in either Phase 1 or Phase 2 will receive the corresponding treatment for that phase (e.g., first-stage or second-stage randomized treatment).

7.1.2

Standard of Care Study Procedures

The oral examination and treatment with silver diamine fluoride, fluoride varnish, and dental sealants are considered part of regular standard of clinical care. All of the included procedures can be expected to be provided outside of the study, but the study specific procedures will modify the order of the procedures that are provided.

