7.4 Concomitant Medications, Treatments, and Procedures

Concomitant medications are not applicable. However, concomitant treatments and procedures that are observed through oral examinations (e.g., care provided by an external dentist, such as evidence of teeth with fillings that were not observed previously) will be noted in EHRs.

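### A new cavity on a previously sound posterior surface that is filled or extracted outside the program is scored as a response, with no new caries

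*Protocol*

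**What the plan says.** Section 4.2.1 of the Protocol gives two primary endpoints: the count of new caries seen, and the share of children with caries, which it equates with nonresponse. Section 7.1.1 sets the operational rule: "Nonresponse will be determined at the second and third post-baseline observational periods by the diagnosis of any dental caries on posterior dentition". That rule covers new lesions on sound teeth and teeth carious at baseline that did not arrest. Caries means ICDAS 5 or 6, an open cavity with visible dentine.

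The same section fixes what the examiner records. For surfaces: "Individual tooth surfaces will be assessed as being intact/sound, sealed, restored, decayed, or arrested". For teeth: "Teeth will be assessed as being present or missing intraorally". No reason for a missing tooth is asked for.

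Section 7.1.1 then adds five design rules. One gives a route to nonresponse without a caries diagnosis: "any patients with atraumatic restorations that are not retained will be considered non-responsive". None mentions restorations or extractions done elsewhere.

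Section 7.4 does foresee outside treatment, naming "care provided by an external dentist, such as evidence of teeth with fillings that were not observed previously", and has it noted in the electronic record. Section 7.6 places no restriction on outside care. Section 10.6.1 says that neither clinicians nor patients can be masked.

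**The concern.** A filling placed elsewhere on a surface that was sound at the last study visit is evidence that prevention failed there. Under the stated rule it has the opposite effect. The surface is now restored, nothing is diagnosed, and the child passes as a responder unless another lesion is open or an atraumatic restoration has been lost. The lesion also drops out of the incidence count even when the child is a nonresponder for another reason.

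This bears on the primary hypothesis in section 10.2, a difference in nonresponse between first-stage assignments. It also bears on who enters second-stage randomisation at visits 2 and 3 (section 7.3.3). The protocol already treats a lost atraumatic restoration as nonresponse because new decay cannot be excluded. A new filling on a formerly sound surface points to decay at least as strongly, yet it scores as success.

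**Working it through.** **How each case is scored under the text**

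- Surface sound at an earlier visit, new cavity, still open at the visit: decayed, so nonresponse and one new lesion.
- The same cavity filled elsewhere before the visit: restored, so no diagnosis, a response and no new lesion.
- The same tooth extracted elsewhere: missing, with the same result. The chart cannot separate this from natural loss of a primary tooth at ages 5 to 13.
- Tooth carious at baseline, then filled elsewhere: ambiguous. It could be read as a failure to arrest, or simply as restored.
- Study atraumatic restoration replaced elsewhere: ambiguous. It could be read as not retained, hence nonresponse.

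The second and third cases are the clear gap.

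**Inputs from the Protocol**

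- Average nonresponse 30%, assumed equal across first-stage arms (10.5).
- 1200 enrolled (5.6), so 420 + 90 + 90 = 600 per first-stage arm (subgroup table).
- Anticipated final N of 840 (10.5), or 420 per arm if split equally.
- Two-sided alpha 0.05 (10.4.1).

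**Input not in the Protocol:** h, the share of nonresponding children whose every failing lesion was treated elsewhere before the visit. It is assumed here at 0 to 20%.

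**The plan's own figure.** Section 10.5 gives a total of 122 for d = 0.5, correlation 0.5, 10% drop-out and power 0.85. A t-based calculation needs 72.8 per arm, rounded to 73. Then 73 × (1 − 0.5²) / 0.9 = 60.8, rounded to 61, and 2 × 61 = 122. The figure reproduces. It does not depend on how outside treatment is scored.

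**Equal hiding.** Observed rate = true rate × (1 − h). With h = 10% in both arms:

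- 0.30 × 0.90 = 0.27.
- Nonresponders fall from 1200 × 0.30 = 360 to 1200 × 0.27 = 324.
- A true difference shrinks by the same factor. For an illustrative 30% vs 22.5%, 7.5 points become 7.5 × 0.90 = 6.75.
- Power of a simple two-proportion test falls from 84% to 79% at 600 per arm, and from 70% to 63% at 420 per arm.
- Type I error stays at 5%.

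**Unequal hiding, true rate 30% in both arms.** With observed rates p1 and p2, mean p̄, d = p1 − p2 and n per arm, se0 = √(2p̄(1 − p̄)/n) and se1 = √((p1(1 − p1) + p2(1 − p2))/n). The probability of rejection is Φ((−1.96·se0 − d)/se1) + 1 − Φ((1.96·se0 − d)/se1).

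| h by arm | Observed | False difference | Rejection, n = 600 | Rejection, n = 420 |
|---|---|---|---|---|
| 10% / 5% | 27.0% / 28.5% | 1.5 points | 8.9% | 7.7% |
| 10% / 0% | 27.0% / 30.0% | 3.0 points | 21% | 16% |
| 20% / 5% | 24.0% / 28.5% | 4.5 points | 43% | 32% |

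**Unequal hiding with a true difference** (30% vs 22.5%). If h is 20% in the higher-rate arm and 5% in the lower, the observed rates are 0.30 × 0.80 = 24.0% and 0.225 × 0.95 = 21.4%, a gap of 2.6 points. With the shares reversed they are 28.5% and 18.0%, a gap of 10.5 points. The distortion can go either way.

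The planned analysis is a mixed logistic model, so the power and rejection figures are only indicative.

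**The case against.** **Much of this can be recovered in analysis.** This is largely right for fillings. Every surface is charted at every visit, section 6.1.10 logs study treatment by tooth, and 7.4 has outside care noted. A change from sound to restored with no study treatment could be derived, and a later analysis plan might do so. But the protocol already states an endpoint and a rule that give the wrong result, and later derivation cannot change who was re-randomised or say why a tooth is missing.

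**The second-stage rule may be deliberate.** Parts of the second-stage treatment act on affected teeth, and a child whose only lesion was filled elsewhere may have none. This stands as a reason not to presume which classification is right for second-stage entry. It does not excuse leaving the case unstated.

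**Counting outside fillings brings its own error.** An outside dentist may fill below the ICDAS 5 threshold, and if families in one arm seek more outside care, counting every filling could inflate failure there. This stands, and it is why a sensitivity analysis is needed.

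A reader might go further and infer that the results are biased between arms, for instance because visible silver diamine fluoride staining sends those families elsewhere. The documents do not support that. Section 2.4.1 does mention psychosocial effects, but it describes staining of carious lesions, and it also reports non-inferior quality of life. Stain-driven care would mainly concern teeth already carious, not new lesions on sound surfaces. The population is described as low-income, in a disease linked to poor access to care, which gives no reason to expect frequent outside treatment. Nor is it right that nonresponse counts caries alone, since a lost atraumatic restoration also counts.

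**Conclusion.** The concern holds for new lesions on previously sound posterior surfaces that are filled or extracted outside the program. As written, 4.2.1 and 7.1.1 score them as no event, although 7.4 expects the fillings to occur. Failure is understated, and if hiding is equal a true difference is attenuated in proportion: 10% hidden turns 30% into 27%, and 360 second-stage entrants into 324.

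This rests on the protocol's 30% and on an assumed hidden share. The documents give no rate of outside care, so the real effect could be negligible. Imbalance between arms is possible because nobody at the chairside or at home is masked, but its size and direction are unknown. The table shows only how sensitive the primary comparison would be. Teeth already carious or arrested, and atraumatic restorations replaced elsewhere, are ambiguous under the text and are not clear errors.

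**What to change.** **Outcome definition (4.2.1).** Count a new restoration on a posterior surface charted sound at an earlier study visit, with no study restoration logged for it, as a caries event for both the binary endpoint and the count. Add a sensitivity analysis that does not count it, because of the treatment threshold.

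**Ambiguous cases.** Analyse both ways, as sensitivity analyses, outside restorations on teeth previously charted carious or arrested, and missing posterior teeth judged to be extracted.

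**Data capture.** Add two coded fields at the existing examination: restored outside the program, and reason for a missing tooth (extracted, exfoliated or unknown). The unknown category matters, because an unmasked examiner often cannot tell at these ages.

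**Second-stage entry.** Reconcile 7.1.1 with 7.4 so that the classification of a child with only outside-treated caries is explicit. No treatment rule is proposed here. If that classification differs from the outcome definition, give the two separate names, since 4.2.1 now equates them.

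The cost is endpoint wording and two fields at an examination already done. The downside is that some outside fillings placed for lesser lesions will count as events. The fields should be in place before visit 2, which the schedule puts in Spring 2027.

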The average annual failure rate for single- and multiple-surface ART restorations in primary molars is estimated to be 5 and 17%, respectively [16], though this may be outperformed by conventional restorations [17]. Like SDF, prior studies of ART in community settings conclude that it is acceptable and effective in socioeconomically deprived groups [18]. More recently, a systematic review and meta-analysis of clinical outcomes of ART restorations in children estimated overall success rate of 71% and 67% after 12 and 24-months, respectively [44]. Operator error was a major contributing factor to the success of ART restorations [44].

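### A lost ART restoration counts as nonresponse without observed decay, and at first stage only the sealant/ART arm receives ART, so binary nonresponse means different things in the two arms

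*Protocol*

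**What the plan says.** Section 7.1.1 determines nonresponse at the second and third observations "by the diagnosis of any dental caries on posterior dentition", meaning new caries on sound teeth or baseline caries that has not arrested. Its list of additional design procedures then treats two kinds of lost material differently:

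- Sealants: "any patients with sealants that are not retained but no decay is indicated will be considered responsive and the sealant will be reapplied".
- Restorations: "any patients with atraumatic restorations that are not retained will be considered non-responsive", the reason given being that freedom from new decay cannot be reliably established in that case.

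The first-stage arms in the same section are "silver diamine fluoride (Trajectory 1) or dental sealants with atraumatic restorations, where indicated (Trajectory 2"). On the SDF arm it adds: "Children in the initial SDF group will receive the treatment on sound posterior dentition and any posterior teeth with untreated decay". ART or SMART reaches that arm only through second-stage assignment, after nonresponse has been declared.

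Section 10.2 states the null hypothesis as equal treatment nonresponse between the first-stage arms. Section 4.2.1 names the count of new caries and person-level caries prevalence as primary endpoints and links prevalence to nonresponse. Section 10.4.2 fits logistic models to caries presence and to nonresponse, and a negative binomial model to caries incidence.

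**The concern.** A first-stage comparison needs one outcome definition for both arms. Here the sealant/ART arm has an additional route to failure, created by the treatment itself. A child whose restoration has come out is a nonresponder even if the examiner sees no decay. A child in the SDF arm with the same lesion at baseline fails only if the examiner finds it not arrested.

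If the two treatments are equally good against caries, this rule alone makes the observed nonresponse rates differ. The difference does not shrink as enrolment grows, so a larger trial is more likely to declare it significant.

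**Working it through.** **The plan's own figure.** Section 10.5 gives a total of 122 for d = 0.5, power 0.85, two-sided alpha 0.05, correlation 0.5 and 10% dropout. With variance factor 1 − 0.5² = 0.75, the normal approximation gives 54 per arm, 108 in total and 108/0.9 = 120. The t-based version gives 55 per arm, 110 in total and 110/0.9 = 122.2. The figure reproduces, so the sample size is not the issue here.

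**Inputs from the protocol**
- Nonresponse of 30%, equal in both arms (10.5).
- Two-sided alpha of 0.05 (10.4.1).
- 1200 enrolled, so 600 per arm; 840 after dropout, so 420 per arm (10.5).
- Annual ART failure of 5% (single-surface) and 17% (multiple-surface) (2.2.2).
- From a meta-analysis, "estimated overall success rate of 71% and 67% after 12 and 24-months, respectively" (2.2.2), so 29% failure at 12 months, the time of Visit 3.

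**Assumption.** The share q of the sealant/ART arm with an ART placed at baseline is not in the protocol. I take 30% as the working value and 10% to 50% as the range.

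**Step 1: added nonresponse.** With true nonresponse p0 and failure f, a child is added if an ART was placed, was lost, and the child had not otherwise failed:

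added = q × f × (1 − p0)

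- f = 5%: 0.30 × 0.05 × 0.70 = 0.0105, or 1.1 points
- f = 17%: 0.30 × 0.17 × 0.70 = 0.0357, or 3.6 points
- f = 29%: 0.30 × 0.29 × 0.70 = 0.0609, or 6.1 points

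This is an upper bound for a given child-level f, because every such loss is taken as decay-free.

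**Step 2: false rejection.** I used a two-sided pooled z-test of p0 against p0 + added. For f = 17% and 600 per arm, the rates are 0.3000 and 0.3357, with mean 0.31785. The pooled standard error is √(2 × 0.31785 × 0.68215/600) = 0.02688 and the unpooled one 0.02686. The upper-tail limit is (1.96 × 0.02688 − 0.0357)/0.02686 = 0.63, giving a probability of 0.26.

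| q = 30%, p0 = 30% | f = 5% | f = 17% | f = 29% |
|---|---|---|---|
| Added points | 1.1 | 3.6 | 6.1 |
| False rejection, 600 per arm | 6.8% | 26% | 61% |
| False rejection, 420 per arm | 6.3% | 20% | 47% |
| Half the losses decay-free, 600 per arm | 5.4% | 10% | 21% |

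**Range over q.** At q = 10% and f = 5%, the addition is 0.10 × 0.05 × 0.70 = 0.35 points and false rejection at 600 per arm is 5.2%. At q = 50% and f = 29%, it is 0.50 × 0.29 × 0.70 = 10.2 points and 96%.

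**The case against.** **The rule has a stated reason.** The protocol says that absence of new decay cannot be robustly determined under a lost ART. ART goes on cavitated lesions and sealants on pits and fissures, so trusting the examination after a lost sealant but not after a lost ART is defensible. A reader might infer that the two rules contradict each other; they need not. What stands is that an undetermined status is scored as failure, and first-stage treatment creates that situation in one arm only.

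**The net direction is open.** A reader might infer that the primary comparison as a whole is biased against the sealant/ART arm. The documents do not support this. A retained ART covers its lesion, so non-arrest there may go unseen, whereas SDF-treated lesions stay exposed. Section 2.2.2 puts SDF arrest after one application at 47% to 90%, leaving 10% to 53% that could be scored not arrested. Only this rule's own contribution has a known sign.

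**Only part of the primary analysis is touched.** The rule changes nonresponse. It does not change caries counts or diagnosed caries presence, which section 10.4.2 models separately. But section 10.2 states the hypothesis on nonresponse, and section 4.2.1 ties prevalence to it.

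**The size is uncertain.** It would be wrong to quote 26% to 61% as the trial's false-positive rate. Those figures rest on an assumed ART share and the two higher failure figures; at 5% failure the rate is 6.8%, close to nominal. Cited failure includes causes other than loss, which overstates the effect; several restorations per child would understate it.

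**Older restorations.** ARTs placed before enrolment could bring the rule into the SDF arm, but randomization should balance these.

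**Second-stage sizing.** Unequal nonresponse departs from the section 10.5 assumption with little consequence: the stated need is 406 against 1200 planned, and extra nonresponders enlarge that comparison.

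**The SAP is not shown.** It may hold a sensitivity analysis, so its absence here is no finding. The endpoint definition, however, is fixed in the protocol.

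**Conclusion.** The point holds in a limited form. Binary nonresponse, on which the first-stage hypothesis is stated, is defined differently in the two arms by a rule that requires no observed decay. With equal true nonresponse of 30% and an assumed 30% of the sealant/ART arm having baseline ART, the upper bound on the rule's own effect ranges from negligible at 5% failure to large at 29%. It remains appreciable at 17% and 29% even if half the losses are decay-free. The true size depends on the ART share, which the protocol does not give, and on how many lost restorations leave no decay.

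**What to change.** Separate the endpoint from the treatment trigger, and leave the rule that sends children to second-stage randomization as it is.

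- In sections 4.2.1 and 10.2, state that the first-stage comparison is tested on examined caries (new or not arrested), and define the prevalence endpoint in 4.2.1 the same way. The data are already collected at each visit: "Individual tooth surfaces will be assessed as being intact/sound, sealed, restored, decayed, or arrested".
- Report, by arm, children whose only ground for nonresponse is a lost ART, with no caries on any other posterior surface.
- Prespecify two bounding analyses: all such children as nonresponders (the current rule), and all as responders.

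Applying ICDAS 5/6 alone to the exposed surface would not be enough, because an unfilled cavity may meet that criterion by its form. The result then turns on the arrest call, which is the judgement the protocol regards as unreliable. The two bounds show how much depends on it.

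The cost is a few sentences and two additional analyses, with no new data and no change in care. The downside is that a few children will be nonresponders for treatment but not for the endpoint, and the arrest call on an exposed ART surface remains uncertain.
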